#### 4.1 Randomization and Blinding

Randomization and blinding will not be applied.

## 4.2 Termination of Study

The study will be terminated if (1) study medication is considered not tolerable even in the lowest dose cohort by  $\ge 2$  of 3 or  $\ge 2$  of 6 evaluable volunteers, (2) the sponsor terminates the study.

The sponsor reserves the right to terminate the study at any time. The appropriate IRB/IEC and regulatory authorities should be informed accordingly.

## 4.3 Dose Delay and Discontinuation Rules

Healthy volunteers will discontinue Careseng 1370 if experiencing DLT or intolerable toxicity. If volunteers in level A, B or C happen to miss or delay dosing not owing to DLT or intolerable toxicity, volunteers may continue the next dosing. If volunteers in level D happen to miss or delay dosing not owing to DLT or intolerable toxicity, volunteers should be withdrawn from the study. For level A, B and C, volunteer who misses dosing and fails to reach 80% of study drug compliance should be withdrawn from the study. For level D, volunteer who misses any dosing should be withdrawn from the study.

If possible, volunteers will be assessed using the procedures planned for the Final visit within 3 days after withdrawal is consented or Careseng 1370 is discontinued.

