#### **3.** STUDY POPULATION

#### 3.1 Volunteers Enrollment

In design of traditional 3+3 paradigm with four candidate dose levels, the number of evaluable healthy volunteers will be up to 24.

Note: A volunteer is considered evaluable if he/she

1. receives any Careseng 1370, and

2. experiences DLT OR completes DLT observation period with at least 80% of study drug compliance and has exposed to Careseng 1370 for at least 4 days (level A, B, and C), OR completes DLT observation period with 100% of study drug compliance (level D).

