#### 6.6 Dosing, Dispense and Retrieve Careseng 1370

Careseng 1370 will be dosed at site and dispensed for taking at home following the table below. Used and unused IP will be returned at the next scheduled visits.

	Day 1	Day 2	Day 3	Day 4	Day 5
Breakfast	Site	Site #	Site	Site #	Site
Lunch*	Site	Home	Home	Home	Site

#Not required for level D; \*Not required for level A and D

Volunteers should take Careseng 1370 for lunch (if there is one) at 4 hours (+ 10 minutes) after taking Careseng 1370 for breakfast on that day. The definition of "dosing at home for lunch" means that subjects leave the site and administer the second dosing somewhere else before lunch except level A and D (off-site dosing).

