#### Final Visit (Day 22 ± 2; Visit 11, or within 3 days after withdrawal)

- Measure body weight
- Perform physical examination
- Assess vital signs
- Conduct 12-lead EKG
- Perform pregnancy test for female volunteers of childbearing potential
- Conduct laboratory tests (with immunology test) (fasting)
- Record adverse events
- Record concomitant medications

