#### Safety Analyses

Adverse events observed after signing informed consent form till exit from study will be coded using Medical Dictionary for Regulatory Activities (MedDRA) using the version agreed by sponsor and will be reported by dose level by System/Organ/Class and Preferred Terms classified in MedDRA as appropriate. The toxicity grade of adverse events will be rated according to definition in Section 8.2. Findings in physical examinations will be displayed for each individual system. Changes from pre-dosing laboratory test results, body weight, EKG and vital signs to applicable post-dosing visits will be analyzed by descriptive statistics and (if applicable) will be presented by transition table for normality (normal, clinically not significant, clinically significant). Findings in 12-Lead EKG and X-ray will be presented by description.

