1.1 Visit Adjustment

Visit 11 is final visit or early withdrawal visit, refer to 14.3 for detail of visit adjustment

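### Protocol 4.3 takes non-compliant volunteers out of the study rather than only off the drug, so capture of new adverse events can stop at about Day 6-8 instead of Day 22

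*Protocol*

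**What the plan says.** Protocol 4.3 describes two different actions. For DLT or intolerable toxicity, the volunteer stops Careseng 1370. For dosing lapses the volunteer leaves the study: at Level D, if "volunteers in level D happen to miss or delay dosing not owing to DLT or intolerable toxicity, volunteers should be withdrawn from the study"; at Levels A-C, a "volunteer who misses dosing and fails to reach 80% of study drug compliance should be withdrawn from the study". Section 3.4 item 7 lists the compliance failure under a permissive *may*.

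In either case 4.3 asks, where possible, for the Final-visit procedures "within 3 days after withdrawal is consented or Careseng 1370 is discontinued". The Final-visit entry in section 7 sets Visit 11 at Day 22 ± 2 "or within 3 days after withdrawal", and SAP 1.1 agrees: "Visit 11 is final visit or early withdrawal visit, refer to 14.3 for detail of visit adjustment".

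On event capture, Protocol 10.2.2 says "Adverse events observed after signing informed consent form till exit from study will be coded". Sections 3.4 and 8.3.1 require an event already present to be followed until it resolves or stabilises. Section 2.1 sets the DLT window as Day 1 to Day 10, and section 4 plans follow-up to Day 22. Under 10.2.1, safety is analysed in everyone who received any drug.

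**The concern.** The primary endpoint is the incidence of adverse events and serious adverse events. SAP 14.3.1.1 reports it as crude event and subject counts with percentages, so a volunteer observed for about a week counts the same as one observed for 22 days. No text keeps a volunteer withdrawn under these rules on the Day 12 or Day 22 schedule, or under observation to Day 10. An event that starts after exit is not sought.

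Two things are at stake. A DLT with onset by Day 10 makes a volunteer evaluable under 3.1 whatever the compliance, so one that begins after exit could go unseen. The volunteer also loses the Day 12 and Day 22 examinations, which include body weight, INR and APTT, the areas of risk named in 1.3.

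**Working it through.** **Plan's own figures.** A compliant volunteer takes the last dose on Day 5 and is followed to Day 22: 22 − 5 = 17 days after the last dose, of which 10 − 5 = 5 lie in the DLT window.

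**Inputs.** Assigned sachets (5.2): A 5, B 10, C 15, D 3 (Days 1, 3 and 5). Compliance = sachets taken / sachets assigned (5.6). Final visit within 3 days (4.3).

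**Assumptions.** The first dose is taken, so the volunteer is in ITT. The rule is acted on the day it is met, meaning the day 80% can no longer be reached at A-C, or the day of the missed or late dose at D. The exit visit is on the last allowed day.

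**Formulas.** Exit = trigger day + 3. DLT days unseen = 10 − exit. Follow-up lost = 22 − exit. All missed-dose patterns were enumerated.

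| Level | First compliance that triggers | Trigger day | Exit day | DLT days unseen | Days short of Day 22 |
|---|---|---|---|---|---|
| A | 3/5 = 60% | 3-5 | 6-8 | 4-2 | 16-14 |
| B | 7/10 = 70% | 2-5 | 5-8 | 5-2 | 17-14 |
| C | 11/15 = 73% | 2-5 | 5-8 | 5-2 | 17-14 |
| D | 2/3 = 67% if missed; 3/3 = 100% if only late | 3 or 5 | 6 or 8 | 4 or 2 | 16 or 14 |

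**Where Day 5 comes from.** It needs a Day 2 trigger. At B that means missing the Day 1 lunch and both Day 2 sachets. At C, Day 2 holds only 3 sachets and 4 must be missed, so the Day 1 lunch must be among them. The Day 1 lunch is a site dose at both levels (6.6).

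**How easily the rule is met.** One wholly missed day leaves 4/5 = 8/10 = 12/15 = 80%, which does not trigger. All A and D doses are given at site; off-site doses are only the B and C lunches on Days 2-4. With every site dose taken, B must miss all three lunches (7/10; exit Day 7) and C two of three (11/15; exit Day 6 or 7). If the lapse is found at the next visit's drug return, add one day.

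**Weight of one volunteer (illustration).** If one replaced volunteer joins 3 or 6 evaluable ones in a cohort's ITT denominator, that volunteer is 1/4 = 25% or 1/7 = 14% of it.

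**Drug stopped for toxicity.** The 3-day visit in 4.3 also runs from drug discontinuation, and 3.4 items 2 and 5 list intolerable symptoms and DLT as grounds for withdrawal. A stop on Day t therefore brings the Final visit to Day t + 3 at the latest.

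**The case against.** The strongest reply is that this will seldom happen. Nearly all doses are supervised, Level D opens only after de-escalation from A, and the documents give no expected number of such withdrawals. The wording also leaves room: 3.4 says *may*, and the early visit is required only where possible. All of that stands and limits the size of the point. It does not remove it, because the specific instruction in 4.3 says *should* and nothing provides for continued observation.

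A reader might infer that safety follow-up ends altogether. It does not: events present at exit are followed, and the exit visit carries the full Final-visit set. Nor does 10.2.2 say that a later event would be ignored if it became known; the gap is that nobody looks for it.

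The DLT loss looks smaller if counted from the last dose. Withdrawn volunteers have 3-5 days after their last dose against 5, a loss of 0-2. But 2.1 defines the window in calendar days, so 2-5 is the figure that matches the protocol. If failing 80% is judged only at the end of the course, exit at A-C is by Day 8 and the loss is at the lower end.

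The risks in 1.3 come from rats dosed for 13 weeks at 1,350 and 2,700 mg/kg/day, and the clotting changes were not seen after recovery. That tempers the clinical weight of the lost visits. SAP Table 14.1.2 would show shortened study duration, but cannot recover unseen events.

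**Conclusion.** The point holds as a matter to correct, at moderate weight. Followed as written, 4.3 ends scheduled assessment and capture of new-onset events at about Day 6-8 (Day 5 only with missed site doses at B or C). That removes 2-5 calendar days of the DLT window and 14-17 days of planned follow-up from a volunteer who remains in the primary-endpoint denominator. These figures assume same-day action and a visit on the last allowed day; an earlier visit loses more, and later action loses less.

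Two further readings are not supported. One is that the 3+3 decision is materially distorted: a withdrawn volunteer with no observed DLT is non-evaluable and enters no count, so only an unseen late DLT could matter. The other is that any slightly late Level D sachet must lead to exit. The word *delay* has no stated limit, and the closing Level D sentence of 4.3 mentions only missed doses, so this needs clearer wording rather than a finding of error.

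**What to change.** In 4.3, 3.4 and the Final-visit text, separate stopping Careseng 1370 from leaving the study:

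- Any volunteer who stops dosing for non-compliance, a missed dose, DLT or intolerable toxicity continues adverse event collection through Day 10 and attends the scheduled Day 12 and Day 22 visits unless consent is withdrawn.
- The early Final visit is kept for those who withdraw consent or cannot continue.
- Non-compliant volunteers without a DLT are still replaced for the MTD decision. A DLT by Day 10 in such a volunteer counts under 3.1 and goes to the DSMB. No new escalation rule is needed, because section 4 already places every escalation decision with the DSMB.
- It would help to say what *delay* means at Level D.

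The cost is a few sentences, up to two already scheduled visits per affected volunteer, and occasionally a fourth evaluable volunteer for the DSMB to consider. The cohort decision is not held up, since a replacement enrolled after the withdrawal reaches Day 10 later than the volunteer replaced.

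The SAP (08-SEP-2022) postdates the expected exit of the last subject (MAR2022). If dosing has ended, the remaining step is to show follow-up duration beside the adverse event counts for any affected volunteer.

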#### 5. TRIAL MATERIALS

#### 5.1 Trial Product

Product name	Careseng 1370
Character	Light yellow granule 4,000 mg/sachet
Composition	
(w/w)	
	-

#### 5.2 Dosage and Administration

Four dose cohorts are employed for Careseng 1370 oral administration in healthy volunteers:

- Dose level A: Careseng 1370 1 sachet before breakfast for consecutive 5 days
- Dose level B: Careseng 1370 1 sachet before breakfast and 1 sachet before lunch for consecutive 5 days
- Dose level C: Careseng 1370 1 sachet before breakfast and 2 sachets before lunch for consecutive 5 days
- Dose level D (modified chort): Careseng 1370 1 sachet before breakfast on 1st, 3rd and 5th days

The duration of dosing time between breakfast and lunch from Day 2 to Day 5 should be as close to those for Day 1. Volunteers should take Careseng 1370 for lunch (if there is one) at 4 hours (+ 10 minutes) after taking Careseng 1370 for breakfast on that day.

Note: Careseng 1370 generally should be taken around 1 hour before respective meal.

#### 5.3 Storage and Drug Accountability

The IP shipping is to be arranged by the sponsor/designee to the study site and to be handled by the investigator/designee or the designated pharmacist for management and dispensation. Careseng 1370 sachets should be stored at controlled temperature of 15 (59°F) to 30°C (86°F). Long-term exposure to bright light should be avoided. All of the used and unused Careseng 1370 sachets will be returned from the clinical site to the sponsor unless prohibited by site policy. Each batch shipped, used, and returned from/to the sponsor to/from the clinical site will be recorded according to date to keep track of the Careseng 1370 sachets with precise details.

#### 5.4 Packaging/Labeling

All medication used in this study will be prepared, packaged, and labeled under the responsibility of a qualified person at sponsor with Standard Operating Procedures (SOPs) of sponsor, Good Manufacturing Practice (GMP) guidelines, ICH GCP guidelines, and applicable local laws/regulations. Careseng 1370 sachets will be packaged in aluminum foil/bags. All aluminum foil/bags for packaging study medication will be labeled with the descriptions of "Clinical trial use only", "Keep out of the reach of children." and "Caution: New Drug --Limited by United States law to investigational use" as well as other required information according to the local regulatory requirements in the local language.

#### 5.5 IP Retrieval and/or Destruction

Used and unused study drug should be returned to the sponsor for destruction unless prohibited by site policy. In this instance, study drug may be destroyed at the study center according to standard institutional procedures after verification for drug accountability has been conducted by the study monitor, Sponsor or representative. Should this occur, a copy of the standard institutional procedure for destroying investigational drugs will be provided to the Sponsor. Upon destruction, a copy of the certificate of destruction must be provided for the Sponsor files and site drug accountability records.

#### 5.6 Dose Dispensing and Assessment of Compliance

Volunteer's compliance will be assessed by the following formula:

# of sachets of study drug actually administered Total # of sachets of study drug assigned at that level × 100%

#### 6. STUDY MEASUREMENTS

#### 6.1 Eligibility

Eligibility should be thoroughly checked by the investigators at Screening visit and Day 1 visit.

If a volunteer is a screen failure, a minimal set of screen failure information is required to ensure transparent reporting of screen failure subjects, to meet the regulatory authority requirement and to respond to queries from regulatory authorities and IRBs/IECs. Minimal information includes demographics, screen failure details, concomitant medication, and any serious adverse event.

Re-screening for volunteer's eligibility will be allowed if the volunteer is willing to participate in the study and one of the following conditions meets:

- If a volunteer consents to participate and meets the eligibility criteria but a delay occurs in starting to participate in due to certain change in situation such that some measurement relevant to eligibility became invalid owing to the delay
- If the cause of screen failure has now resolved or adequately treated such that volunteer's conditions have now stabilized
- If there is an alternative manner to indicate that the volunteer may be suitable.

In these situations,

- A new eCRF will be used
- A new Screening number will be assigned to the person
- The person will be marked as having been re-screened on both the eCRF and the source document.
- The old eCRF will be completed as fully as possible following eCRF completion guide and data on the old eCRF is not copied to the new eCRF.
- The volunteer needs to sign a new ICF as part of the screening procedure.

It is not appropriate to re-screen a volunteer if he/she has previously failed to meet the eligibility criteria and no further changes or treatments have been able to indicate that the volunteer may be suitable.

Volunteer may be re-tested/measured for procedures relevant to causes of screen failure if investigator considers such causes can be resolved soon.

#### 6.2 Medical History

General medical history within 6 months should be recorded at Screening visit. Histories of psychiatric disorder, left ventricular outflow obstruction, HIV infection or hepatitis B or C, and major surgery will be recorded on a lifetime basis.

#### 6.3 Medication History

Previous medications should only be recorded up to 4 weeks before Screening visit.

#### 6.4 Demographics, Physical Examination, Vital Signs, Height, and Body Weight

Demographics including gender, date of birth, and race will be collected at Screening visit.

Physical examination conducted in this study will include the following items: general appearance, skin, eyes, ears, nose, throat, head and neck, heart, chest and lungs, abdomen, extremities, lymph nodes, musculoskeletal, neurological, and other.

Vital signs measurement will consist of systolic/diastolic blood pressure, respiratory rate, pulse rate or heart rate, and body temperature. Respiratory rate, pulse rate or heart rate and blood pressure (systolic/diastolic) will be obtained after the volunteer has been at rest for at least 5 minutes in a sitting position.

Height will be recorded only at Screening visit. Body weight will be recorded at all scheduled visits except visit 8 and 9.

Healthy volunteers should come fasted, specific for pre-dose measurement of physical examination, vital signs, and body weight prior to Careseng 1370 administration during dosing period (Day 1 to Day 5).

## 6.5 Laboratory Examination and PK sampling

Laboratory examination to be measured in this study will consist of the following:

Hematology: hemoglobin, hematocrit (Hct), RBC, WBC (with differential), absolute neutrophil count (ANC), lymphocyte count, platelets, international normalized ratio (INR) of prothrombin time (PT), activated partial thromboplastin time (APTT).

Immunology: CD3, CD4, CD8, CD19, CD16 and CD56 assessments, presented as CD3+, CD3+/CD4+, CD3+/CD8+, CD19+, CD16+/CD56+, and CD4/CD8 ratio.

Biochemistry: AST, ALT, albumin, alkaline phosphatase (ALP), total bilirubin, creatinine, blood urea nitrogen (BUN), c-reactive protein, total protein, gamma glutamyl transferase ( $\gamma$ -GT), blood glucose, uric acid, total cholesterol, triglycerides, sodium, potassium, calcium, magnesium, phosphorus, amylase, lipase.

Urinalysis: pH, protein, RBC, WBC, casts.

Healthy volunteers should come fasted for laboratory examinations at all scheduled time points, except 8 hours post-first dose on Day 1, and 4 hours post-dose on Day 5.

The definition of "pre-dose PK blood sampling" means blood collection for PK prior to the first dose of that day (level A-D), or at scheduled visits without dosing of that day (level D). The definition of "post-dose" means the PK blood sampling after the 1st dose on Day 5. PK blood samplings at scheduled time points will be collected and examined for the concentration of 20(S)-protopanaxadiol (PPD) and its metabolites, and analyzed for PK parameters.

#### 6.6 Dosing, Dispense and Retrieve Careseng 1370

Careseng 1370 will be dosed at site and dispensed for taking at home following the table below. Used and unused IP will be returned at the next scheduled visits.

	Day 1	Day 2	Day 3	Day 4	Day 5
Breakfast	Site	Site #	Site	Site #	Site
Lunch*	Site	Home	Home	Home	Site

#Not required for level D; \*Not required for level A and D

Volunteers should take Careseng 1370 for lunch (if there is one) at 4 hours (+ 10 minutes) after taking Careseng 1370 for breakfast on that day. The definition of "dosing at home for lunch" means that subjects leave the site and administer the second dosing somewhere else before lunch except level A and D (off-site dosing).

#### 6.7 12-Lead EKG and Chest X-Ray

12-Lead EKG measurement will at least include rhythm, ventricular rate, PR interval, QRS duration, QT and QTc intervals. Healthy volunteers should come fasted, specific for pre-dose measurement of 12-Lead EKG prior to Careseng 1370 administration during dosing period (Day 1 to Day 5).

Chest X-Ray will only be performed at Screening visit and per investigator's discretion for unscheduled visit if necessary.

#### 6.8 Dispense and Retrieve Diary

The information to be collected in diary should contain at least number of sachets taken at home of Day 2 to Day 4 and each dosing time.

#### 6.9 **Pregnancy Test**

Volunteer's pregnancy status should be checked by serum or urine pregnancy test at Screening and Final visit and any time if investigator or volunteer suspects the volunteer is pregnant.

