Administration	schedule (level A, B, and C: consecutive 5 days; level D: 1 st , 3 rd and 5 th days), or until experiencing DLT, unacceptable toxicity, his/her loss of follow-up, or early withdrawal, whichever comes first.
Recruitment	Local posters are planned for recruitment of volunteers. Other
Strategies	acceptable methods of recruiting volunteers may include advertisement in magazine and social media, which should be submitted to IRB for review and approval before the recruitment efforts begin.
Volunteer	This study will be done in healthy volunteers administered with
Assignment	Careseng 1370 1, 2, or 3 sachets per day (level A, B, and C), or Careseng 1370 1 sachet on 1 st , 3 rd and 5 th days (level D) before meal in the conventional 3+3 design. No volunteer is allowed to be assigned to more than 1 dose level.
Study Visits	Screening visit: within 2 weeks before Day -1 (inclusive)
	Hospitalization:
	- Day -1: registration of hospitalization in the evening
	Dosing visits:

- Day 1: approximately 24 hours of hospitalization (pre-dose PK blood sampling and dosing at site for breakfast and lunch)
- Day 2: discharge from hospitalization (pre-dose PK blood sampling and dosing (if scheduled) at site for breakfast and at home for lunch)
- Day 3 pre-dose PK blood sampling and dosing at site for breakfast and at home for lunch
- Day 4: pre-dose PK blood sampling and dosing (if scheduled) at site for breakfast and at home for lunch. Registration for hospitalization after planned dosing (if scheduled) on Day 4

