#### **3.3** Exclusion Criteria

Any volunteer meeting any of the exclusion criteria will be excluded from study participation:

1. Volunteer who has a history or evidence of a medical condition that would expose them to a risk of a significant adverse event or interfere with the assessments of safety or pharmacodynamics variables during the course of the trial, including but not limited to hepatic, renal, respiratory, cardiovascular, endocrine, immune, neurological, musculoskeletal or hematological disease as determined by the clinical judgment of the investigator

- 2. Volunteer has received any other investigational agent within 4 weeks prior to the first dose of study drug
- Volunteer has taken or potentially takes any herbal medication/supplements/medicinal food, prescription medication and/or over-thecounter medication within 2 weeks prior to the first dose of study drug
- 4. Volunteer has consumed alcohol, caffeine, grapefruit juice, nicotine, phosphorous supplement, calcium supplement, or food rich in calcium within 24 hours prior to the first dose of study drug
- 5. Female volunteer of childbearing potential who:
  - is lactating; or
  - has positive pregnancy test result at eligibility checking; or
  - refuses to adopt at least two forms of birth control (at least one of which must be a barrier method) from Screening visit to Final visit.

Note: Acceptable forms include:

- 1. Established use of oral, injected or implanted hormonal methods of contraception.
- 2. Placement of an intrauterine device (IUD) or intrauterine system (IUS).
- 3. Barrier methods of contraception: Condom OR Occlusive cap (diaphragm or cervical/vault caps)
- 6. Male volunteer with female spouse/partners who are of childbearing potential refuses to adopt at least two forms of birth control (at least one of which must be a barrier method) from Screening visit until Final visit
- 7. Known or suspected allergy or hypersensitivity to any ingredients of study product
- 8. With history of stroke, myocardial infarction, or Coronary Artery Bypass Graft (CABG) surgery within the last 6 months prior to the screening visit
- 9. With history of cardiac failure (New York Heart Association class 2 or above), unstable angina, or life-threatening arrhythmia within the last 6 months prior to the screening visit
- With blood pressures as systolic blood pressure < 90 mmHg or > 170 mmHg or diastolic blood pressure < 50 mmHg or > 120 mmHg at eligibility checking

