#### Screening (Days -14 to -1; Visit 1)

- Obtain informed consent form
- Assign volunteer identifier
- Obtain medical history
- Collect volunteer demographics data
- Record medication history (including concomitant medications)
- Measure height
- Measure body weight
- Perform physical examination
- Assess vital signs
- Conduct 12-lead EKG (test performed within 14 days are acceptable)
- Perform pregnancy (urine or serum test for female volunteers of childbearing potential)
- Conduct laboratory tests (with immunology test) (test performed within 14 days are acceptable) (fasting)
- Conduct chest X-ray (test performed within 14 days are acceptable)
- Assess the volunteer's eligibility for the study (inclusion/exclusion criteria)
- Record adverse events
- Dispense diary

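### The Day 1 pregnancy exclusion rests on a Screening test that is 1 to 14 days old, so a repeat test before the first dose is worth adding

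*Protocol*

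**What the plan says.** Exclusion 5 (Protocol 3.3) removes a woman of childbearing potential who "has positive pregnancy test result at eligibility checking". Section 6.1 fixes when that is: "Eligibility should be thoroughly checked by the investigators at Screening visit and Day 1 visit".

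On testing, 6.9 says "Volunteer's pregnancy status should be checked by serum or urine pregnancy test at Screening and Final visit". The same sentence also allows an unscheduled test whenever the woman herself or the investigator has reason to suspect a pregnancy. Section 3.4, criterion 4, repeats this rule and makes pregnancy from Screening to the Final visit a ground for withdrawal. In Section 7 the test is listed at Screening and at the Final visit. The Day -1 entry holds only admission. The Day 1 pre-dose list includes an eligibility assessment but no pregnancy test.

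Footnote 1 of the schedule of assessments explains the Day 1 check. It uses that day's body weight, physical examination, vital signs and EKG, together with other information from Screening. The same footnote allows Screening to take place on Day -1.

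On contraception, Exclusion 5 also removes a woman who "refuses to adopt at least two forms of birth control (at least one of which must be a barrier method) from Screening visit". That requirement ends at the Final visit.

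**The concern.** The pregnancy exclusion is applied twice, but only the first application has a test behind it. On Day 1 the investigator has the Screening result and nothing newer unless someone suspects pregnancy. The contraception rule starts at Screening, so it does not cover a conception in the days just before. Such a pregnancy could be too early to show at Screening and could have become detectable by Day 1.

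At stake is exposure of an unrecognised early pregnancy to the full dosing course, in a study that offers volunteers no benefit (Protocol 1.3). The withdrawal rule for pregnancy has no scheduled test that could trigger it before or during dosing. The next one is at the Final visit.

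**Working it through.** The plan gives no figure to reproduce. The check is a day count and a comparison of sections.

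**Age of the result at first dose**
- Inputs: the Screening window of Day -14 to Day -1 (Protocol Section 7) and the study-day rule in the SAP listings instructions, item 5. Before dosing, study day = date minus first-dose date; from first dose onward 1 is added, so there is no Day 0.
- Screening on Day -1: the result is 1 day old on Day 1.
- Screening on Day -14: the result is 14 days old on Day 1.
- The Protocol Summary instead describes Screening as within 2 weeks before Day -1. If that is counted back from Day -1, the earliest day is Day -15 and the maximum is 15 days. The Section 7 window gives 1 to 14 days, which is used here.

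**Is a wait of several days realistic?**
- Section 4 requires at least 5 days between the Day 1 of successive volunteers among the first three in a cohort.
- The third volunteer therefore starts at least 5 + 5 = 10 days after the first. If the three are screened together and the first is dosed the next day, the third volunteer's result is at least 1 + 10 = 11 days old, which is inside the window.

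**Same timing phrase, two exclusions**
- Exclusion 10 (blood pressure) is also judged when eligibility is checked. Vital signs are measured again pre-dose on Day 1, so that exclusion has fresh data on both occasions.
- Exclusion 5 (pregnancy test) has fresh data at Screening only. On Day 1 the earlier result is carried forward under footnote 1.

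**With a repeat test**
- Age of the result at first dose: 1 day if done at Day -1 admission, 0 days if done on Day 1 pre-dose, against 1 to 14 days now.

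**The case against.** The strongest reply is that the carry-forward is a written rule. A reader might infer that Exclusion 5, 6.1 and 6.9 cannot all be followed. They can, because footnote 1 says that the Day 1 check uses Screening information for items not repeated that day. That stands, and it makes this a design gap with loose wording, not a contradiction.

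A reader might also conclude that the Day 1 application of Exclusion 5 is empty. It is not: lactation and refusal of contraception belong to the same criterion and can be reassessed without a test.

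Nor do the documents support saying that a pregnancy will be missed. Testing on suspicion is allowed at any time. Two contraceptive methods, one a barrier, are required from Screening, and where a hormonal method is used its use must already be established. The wait can be as short as one day. Whether a given conception would be negative at Screening and positive by Day 1 depends on assay sensitivity and timing, which the documents do not give.

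The interval between the two scheduled tests can reach 14 + 23 = 37 days (Day -14 to Day 24), but that overstates the point. The last 23 of those days follow the first dose, and a further pre-dose test would not shorten them.

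Finally, Section 7 accepts EKG, laboratory and chest X-ray results up to 14 days old, so the tolerance is not peculiar to pregnancy. That is fair. Still, on-suspicion testing needs someone to suspect a very early pregnancy, and contraception from Screening cannot act on a conception before it.

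**Conclusion.** The point holds as a modest safety improvement. The only scheduled pre-dose pregnancy test is at Screening, 1 to 14 days before the first dose, and the Day 1 eligibility check relies on it. A pregnancy conceived shortly before Screening may therefore go undetected before dosing.

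This assumes that such a pregnancy can be missed at Screening and become detectable within the window. The documents do not allow the frequency to be estimated: they give no assay performance, no count of women of childbearing potential and no distribution of the Screening-to-dose interval. No endpoint, dose-limiting-toxicity rule or statistical figure changes.

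**What to change.** Reconcile Exclusion 5, 6.1, footnote 1 and 6.9 so that they state which pregnancy result the Day 1 check uses, and make it a current one. Keep the Screening test. For women of childbearing potential, add either a urine test at Day -1 admission or Day 1 pre-dose, or a serum test at the existing Day 1 pre-dose blood draw. The result should be known before the first dose. Where Screening takes place on Day -1, its test can serve. Update 6.9, 3.4 criterion 4, the Day -1 or Day 1 pre-dose list and the pregnancy row of the schedule to match.

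The test should be repeated, not moved. Moving it would remove the only scheduled pregnancy test from the visit that includes the chest X-ray.

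The cost is one extra test per woman of childbearing potential, who is already admitted on Day -1. The protocol plans around 29 recruits in all, so the total is around 29 tests even if every recruit were in that group. An occasional volunteer would be excluded at admission after the rest of Screening had been done. A repeat test has its own early blind spot, so it narrows the gap without closing it.
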